### 6.2 Treatment Regimens

Treatment regimens are described in Protocol Section 5.1 as ETV treated subjects (ETV) given a starting dose of 0.015 mg/kg up to a maximum dose of 0.5 mg and PBO subjects.

Treatment regimens are defined as follows:

- As-randomized refers to the treatment regimen assigned at randomization. Accrual and efficacy results are presented as-randomized.
- As-treated refers to the actual treatment regimen received. Subjects who receive the incorrect study therapy for the entire period of treatment are grouped according to the treatment regimen associated with the incorrect study therapy. Otherwise, subjects are grouped according to their randomized treatment regimen. Subjects who never receive study therapy have missing as-treated treatment regimen. Results for subject disposition, demographics, baseline characteristics, safety, and PK parameters are presented as-treated. Furthermore, important safety events that occur while a subject is on an incorrect treatment regimen are specifically discussed in the text of the Clinical Study Report.

If a subject receives at least 1 dose of drug in the randomized regimen, then the as-randomized treatment regimen is equal to the as-treated treatment regimen. If  $\geq 5\%$  of treated subjects have as-randomized regimen different than as-treated regimen, summaries are presented by both treatment regimens for select endpoints (see [Section 7](#)).

### 6.3 Populations for Analyses

- **Enrolled subjects** are those who sign an informed consent form and are assigned a Patient Identification number (PID). This cohort is used to assess subject disposition, deaths and serious adverse events during the **pre-treatment period**.
- **Randomized subjects** are enrolled subjects who receive a treatment assignment from the central randomization center. This cohort is used to assess subject status and accrual.
- **Treated subjects** are randomized subjects who receive at least 1 dose of study therapy. This cohort is used to assess all data domains.
  - **Primary cohort** is defined as at least the first 123 subjects randomized and treated. The Primary Cohort is used for the primary analyses.
- **Off-treatment follow-up subjects** are treated subjects who discontinue study therapy and have at least 1 of the following assessments during the **off-treatment follow-up period** (see [Section 6.1](#)): death date if it exists; adverse event onset date; HBV related diagnosis date; vital signs date; physical measurement date; physical exam date; neurologic exam date; laboratory test date (safety, pregnancy, serology and virology); liver biopsy date; Tanner staging date. This cohort is used to assess safety during the off-treatment follow-up period.
- **Long-term follow-up subjects** are treated subjects who discontinue study therapy and have at least 1 of the following assessments during the **long-term follow-up period** (see [Section 6.1](#)): death date if it exists; adverse event onset date; HBV related diagnosis date; vital signs date; physical measurement date; physical exam date; neurologic exam date; laboratory test date (safety, pregnancy, serology and virology); liver biopsy date; Tanner staging date. This cohort is used to assess safety during the long-term follow-up period.
- **Alternative ETV follow-up subjects** are treated subjects who discontinue study therapy, receive at least 1 dose of alternative ETV therapy, and have at least 1 of the following assessments during the **alternative ETV follow-up period** (see [Section 6.1](#)): death date if it exists; adverse event onset date; HBV related diagnosis date; vital signs date; physical measurement date; physical exam date; neurologic exam date; laboratory test date (safety, pregnancy, serology and virology); liver biopsy date; Tanner staging date. This cohort is used to assess safety during the alternative ETV follow-up period.

- **Year 2 Efficacy Cohort** is treated subjects grouped as-randomized and according to observed Week 48 seroconversion status: ETV, PBO, ETV S48, PBO S48, ETV NS48 and PBO NS48 (S = seroconverter; NS = non-seroconverter). All treated subjects are included in ETV and PBO.
  - **Year 2 Primary Efficacy Cohort** is treated subjects in both Primary and Year 2 Efficacy Cohorts.
- **Year 3 Efficacy Cohort** is observed Week 48 non-seroconverters grouped as-randomized according to observed Week 96 seroconversion status: ETV S96, ETV NS96, PBO S96 and PBO NS96.
- **Year 4 Efficacy Cohort** is PBO-randomized observed non-seroconverters at both Weeks 48 and 96 who seroconverted at Week 144.
- **All ETV Efficacy Cohort** is treated as-randomized ETV subjects and PBO-randomized subjects who received open-label ETV.
- **Post-Year 1 Efficacy Cohort** is treated subjects grouped as-randomized: ETV, PBO, PBO subjects who only received blinded PBO (PBO BL), PBO subjects who received open-label ETV (PBO OL), and All ETV (ETV and PBO OL combined; see previous bullet).
- **Year 2 Safety Cohort** is treated subjects grouped as-treated: ETV, PBO subjects who only received blinded PBO (PBO BL), and PBO subjects who received open-label ETV (PBO OL). In addition, subjects must have received open-label ETV or > 54 weeks of study therapy (the upper bound of the Week 48 visit window; see [Sections 7.4.1](#) and [8.4](#)).
- **All ETV Safety Cohort** is as-treated ETV subjects and as-treated PBO subjects who received open-label ETV.
- **Post-Year 1 Safety Cohort** is treated subjects grouped as-treated: ETV, PBO, PBO subjects who only received blinded PBO (PBO BL), PBO subjects who received open-label ETV (PBO OL), and All ETV (ETV and PBO OL combined; see previous bullet).

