4 INVESTIGATIONAL PLAN

4.1 Study Design and Duration

[figure not shown]
This is a comparative, randomized, double-blinded, placebo-control, multicenter study, assessing the efficacy and safety of oral ETV in pediatric subjects with chronic HBV infection who are HBeAg-positive and nucleos[t]ide naive (< 12 weeks of prior therapy with any nucleos[t]ide antiviral agent with activity against hepatitis B virus). Chronic HBV-infected children and adolescents from 2 to < 18 years of age will be enrolled. Approximately 180 subjects will be randomized 2:1 to ETV or placebo (PLB) for a maximum of 96 weeks of blinded therapy, with the analysis of the primary endpoint at Week 48 to be conducted for the first 123 treated subjects. The randomization will be stratified by age group (2 to ≤ 6 yrs; > 6 to ≤ 12 yrs; > 12 to < 18 yrs). To ensure adequate representation, the target enrollment will be 30 subjects for each age group, with a minimum requirement of 18 subjects. At Week 52 an assessment of HBeAg seroconversion shall be performed based on Week 48 serology results. At the Week 52 assessment, all subjects who achieve HBeAg seroconversion will remain on blinded therapy through Week 96; subjects without HBeAg seroconversion will be switched to open-label ETV. Thereafter, assessment of HBeAg seroconversion shall be conducted at study Weeks 100 and 148 during the open-label treatment. Study subjects who achieve HBeAg seroconversion during open-label ETV at the respective assessment time points shall receive up to an additional 48 weeks of study treatment for consolidation. Open-label ETV may therefore be continued up to Week 144 in ETV

randomized subjects and Week 192 for placebo randomized subjects. All randomized study subjects who do not achieve HBeAg seroconversion will receive a maximum of 96 weeks of study ETV therapy (Figure 4.1).

After completing the blinded treatment or the open-label phase, all subjects will be followed in an observational long-term follow up (LTFU) phase until they complete a total of 5 years of study participation from the start of blinded treatment.

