4.1.1 Subject Management Decisions

Assessment of HBeAg seroconversion will be done, as needed, at Study Weeks:

- 52 (based upon Week 48 result);
- 100 (based upon Week 96 result); and
- 148 (based upon Week 144 result).

The investigators shall conduct the assessment of HBeAg response status at the assessment time points; this will be cross checked centrally by the BMS Medical Monitor/Protocol Manager. Subjects achieving HBeAg seroconversion shall initiate consolidation therapy for an additional 48 weeks as follows:

- At Week 52 (consolidation using blinded therapy to Week 96; 48 weeks counting from Week 48)
- At Week 100 (consolidation using open-label ETV to Week 144; 48 weeks counting from Week 96)
- At Week 148 (consolidation using open-label ETV to Week 192; 48 weeks counting from Week 144)

Subjects who achieve HBeAg seroconversion and revert back to HBeAg-positivity or develop HBeAg-negative CHB shall be managed as follows:

- Any subject who achieves HBeAg seroconversion by the Week 48 assessment and reverts to HBeAg-positive status before reaching Week 96 will be treated with open-label ETV until study Week 144, and then will stop study therapy and proceed to the LTFU phase;
- Any subject who achieves HBeAg seroconversion after the Week 48 assessment, who reverts back to HBeAg-positive status shall stop study treatment, if applicable, and be treated at the discretion of the investigator in consultation with the BMS Medical Monitor.
- Subjects who develop HBeAg-negative CHB (absence of HBeAg, presence of anti-HBe antibodies, active viral replication [HBV DNA by PCR assay $\geq 10,000$ copies/mL] and biochemical or histological evidence of hepatitis) shall be managed at the discretion of the investigator in consultation with the BMS Medical Monitor.

Study treatment (ETV and placebo) shall be provided during the blinded and open-label study treatment phases. Rescue open-label ETV shall be provided to subjects who experience extreme elevations of ALT due to acute exacerbations of CHB upon investigator request and approval by the Central Medical Monitor (see section 4.1.2).

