## **7.6 Safety**

The investigators determine the intensity of AEs and the relationship of AEs to study therapy. The investigators' terms are coded and grouped by system organ class using the latest version of the Medical Dictionary for Regulatory Activities (MedDRA) in production at BMS.

In order to account for AEs with multiple occurrences in the same subject, AE records are collapsed for each subject and preferred term when records have the same onset date, or when records are contiguous or overlapping (see [Section 8.10](#)). All AE presentations are based on collapsed records.

AEs are presented by system organ class and preferred term, both in descending order of incidence on ETV, unless specified otherwise.

AE presentations include both non-serious and SAEs as defined in the protocol, unless specified otherwise. If a subject had an AE with different intensities during the study period, then only the greatest intensity is reported.

On-treatment safety is assessed for the following 3 cohorts (see [Sections 6.1](#) and [6.3](#)):

- Through Week 48 on blinded therapy for treated subjects
  - ETV and PBO are assessed on treatment up to the Week 48 cut, ie, the earlier of (a) 54 weeks, the upper bound of the Week 48 visit window (see [Section 8.4](#)), and (b) the first dose of open-label ETV.
- After Week 48 on blinded therapy or on open-label ETV through Week 96 for the Year 2 Safety Cohort

- ETV, PBO BL and PBO OL are assessed on treatment after the Week 48 cut and up to 102 weeks, the upper bound of the Week 96 visit window (see [Section 8.4](#)).
- On ETV treatment for All ETV Safety Cohort

Note that AEs with onset on the first day of study therapy are considered on treatment, AEs with onset on the first day of ETV are considered on ETV treatment and AEs with onset on the first day of open-label ETV are considered on open-label ETV.

Follow-up safety is assessed for the following 3 cohorts (see [Sections 6.1](#) and [6.3](#)):

- During off-treatment follow-up for off-treatment follow-up subjects in the Post-Year 1 Safety Cohort
- During long-term follow-up for long-term follow-up subjects in the Post-Year 1 Safety Cohort.
- During alternative ETV follow-up for alternative ETV follow-up subjects in the Post-Year 1 Safety Cohort (select endpoints only).

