For PBO-treated subjects who receive open-label ETV, baseline is used during blinded dosing, while ETV baseline is used during open-label ETV dosing.

Laboratory abnormalities by toxicity grade (Grade 1 - 4; Grade 3 - 4) are also summarized by treatment regimen and EOD status (all, normal, abnormal) for the first 2 follow-up cohorts: (1) off-treatment follow-up for off-treatment follow-up subjects in the Post-Year 1 Safety Cohort; (2) long-term follow-up for long-term follow-up subjects in the Post-Year 1 Safety Cohort.

Laboratory abnormalities by toxicity grade (Grade 1 - 4; Grade 3 - 4) are also summarized by treatment regimen during alternative ETV follow-up for alternative ETV follow-up subjects in the Post-Year 1 Safety Cohort.

Emergent laboratory abnormalities by toxicity grade (increased to Grades 1, 2, 3 and 4) are also summarized analogously by treatment regimen and EOD status for the first 2 follow-up cohorts. Emergent abnormalities are those with a higher toxicity grade than the EOD toxicity grade.

Select laboratory elevations and abnormalities are summarized relative to the EOD value for the 3 follow-up cohorts. In addition, elevations of liver function tests (including ALT flares, defined as ALT > 2 x reference and > 10 x ULN) during the follow-up periods are summarized using the reference value (REF) (ie, minimum of the baseline and EOD values) for the 3 follow-up cohorts. Note that for PBO-treated subjects who receive open-label ETV, reference is the minimum of the ETV baseline and EOD values.

ALT multiples of ULN and HBV DNA values are plotted over time for each subject who had an ALT flare on study. The duration of an ALT flare is measured from the first ALT measurement meeting the ALT flare criteria to resolution, defined as (1) the first ALT  $\leq$  baseline or  $\leq 5$  x ULN on treatment, or (2) the first ALT  $\leq$  reference or  $\leq 5$  x ULN during follow-up. If (1) and (2) are not met, an ALT flare is considered unresolved, and the last ALT measurement is used to estimate duration.

The time to and duration of ALT flares (weeks) during off-treatment follow-up are summarized for off-treatment follow-up subjects in the Post-Year 1 Safety Cohort (limited to ETV, PBO OL, and All ETV). Analyses are based on the first ALT flare during off-treatment follow-up.

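### Year 2 safety tables put blinded-placebo time before a late switch into the open-label column (PBO OL) and remove the child from PBO BL because of a later event

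*SAP*

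**What the plan says.** SAP 6.3 groups the Year 2 Safety Cohort as-treated. Besides the ETV column there is one for placebo children given blinded placebo alone (PBO BL). A third column, and the entry rule for the cohort, are worded thus: "PBO subjects who received open-label ETV (PBO OL). In addition, subjects must have received open-label ETV or > 54 weeks of study therapy". This third label carries no date limit.

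SAP 7.6 sets the period: "ETV, PBO BL and PBO OL are assessed on treatment after the Week 48 cut and up to 102 weeks". That end point is the top of the Week 96 window. The Week 48 cut is "the earlier of (a) 54 weeks, the upper bound of the Week 48 visit window"; its other limb is the first open-label ETV dose. The period is described as "After Week 48 on blinded therapy or on open-label ETV through Week 96 for the Year 2 Safety Cohort".

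The protocol creates late switchers by design. At the Week 52 assessment, "all subjects who achieve HBeAg seroconversion will remain on blinded therapy through Week 96" (Protocol 4.1). Under Protocol 4.1.1, a Week 48 seroconverter who "reverts to HBeAg-positive status before reaching Week 96 will be treated with open-label ETV until study Week 144". SAP Appendix 1 also lists, as a deviation, blinded therapy beyond 54 weeks in a child who had not seroconverted at Week 48. Such a child could also switch late.

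**The concern.** The column is fixed per child by something that may happen well into the period, while the period itself starts earlier. For a late switcher, the stretch from week 54 to the first open-label dose is spent on blinded placebo but is tabulated under PBO OL.

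HBeAg reversion is the trigger for the switch. If it is accompanied by an ALT rise or an adverse event (plausible, but not quantified in the documents), that event occurs on placebo and is reported under the open-label label. SAP 7.6 reports only the greatest AE intensity in the period, and SAP 7.6.6.1 the highest toxicity grade, so a placebo-phase event can become the child's only PBO OL entry. PBO BL, the only placebo column in Year 2, loses the same child.

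The report could also disagree with itself. The All ETV Safety Cohort counts from first active ETV (SAP 6.1, 7.6), so it would omit an event that the Year 2 table shows under PBO OL.

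**Working it through.** The plan states no figure on this point. The check applies its rules to one child and then estimates scale.

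**One child.** A placebo child seroconverts at Week 48, reverts, and starts open-label ETV at Week 72 (assumed).
- Week 48 cut = min(54, 72) = 54 weeks.
- Column = PBO OL, because open-label ETV was received.
- Time counted = 102 − 54 = 48 weeks.
- Placebo part = 72 − 54 = 18 weeks (18/48 = 37.5%); ETV part = 102 − 72 = 30 weeks.
- A switch at Week 60 or Week 84 gives 60 − 54 = 6 or 84 − 54 = 30 placebo weeks.

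An ordinary Week 52 switcher is placed correctly. The visit window is ±10 days (Protocol Table 6.1), so the latest visit is at 52 + 10/7 = 53.4 weeks. That is before 54, and the cut becomes the first open-label dose.

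**Does another provision repair it?**
- SAP 7.6.6.1 says "baseline is used during blinded dosing, while ETV baseline is used during open-label ETV dosing". That changes the laboratory reference value, not the column.
- The SAP 7.6 note that an AE starting on the first open-label day counts as open-label classifies that day only.
- SAP 8.9 derives the first open-label dose date and says it separates blinded from open-label measurements, but no rule uses it to re-assign Year 2 columns.
- As-treated in SAP 6.2 is a label for the whole subject.

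**How many children.** Inputs are 60 placebo children (Protocol synopsis); 10% drop-out per year and 10% placebo seroconversion (Protocol 8.1); and 3 of 57 seroconverting on placebo in the cited pediatric study (Protocol 8.1, SAP 5). The plan's own chain reproduces: 20 × 0.9 = 18; 18 × 0.9 = 16.2 (stated as 16); 16 × 0.9 = 14.4 (stated as 14).
- Reach Week 48: 60 × 0.9 = 54.
- Stay on blinded placebo: 54 × 3/57 = 2.8, or 54 × 0.10 = 5.4; about 3 to 5.
- Switch near Week 52: 54 − 2.8 = 51.2, or 54 − 5.4 = 48.6.

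**Size, with an assumed reversion fraction r and switch week w.** The documents give neither. Take r = 25% to 100% and w = 60 to 84. S is the number of seroconverters and M the number of Week 52 switchers.
- Misplaced share of PBO OL time = S·r·(w − 54) / [50·M + 48·S·r], where 50 = 102 − 52.
  - Smallest: 2.84 × 0.25 × 6 = 4.3, divided by 51.2 × 50 + 0.71 × 48, is 0.2%.
  - Largest: 5.4 × 30 = 162, divided by 48.6 × 50 + 5.4 × 48 = 2,689, is 6.0%. This needs every placebo seroconverter to revert.
- Misplaced share of all blinded-placebo time after week 54 = r(w − 54) / [r(w − 54) + (1 − r) × 42], where 42 = 96 − 54.
  - r = 25%, w = 60: 1.5/33 = 4.5%.
  - r = 50%, w = 84: 15/36 = 41.7%.
  - r = 100%: PBO BL is empty.
- By head-count, one late switcher of 5 is 20% of the children on blinded placebo; two of 3 is 67%.
- One misplaced event among about 50 PBO OL children is 1/50 = 2 percentage points.

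**The case against.** These are descriptive tables with no planned test. PBO OL is a separate column from ETV, and the period is openly labelled as mixing blinded and open-label therapy. Reliable analyses exist alongside: the randomized Week 48 tables stop at 54 weeks or first open-label dose, the All ETV tables exclude placebo time, and SAP 7.6.6.1 plots ALT and HBV DNA over time for every child with a flare. PBO BL would be a handful of selected seroconverters even after a correction. All of this stands and limits the importance of the point. It does not put the events in the right column.

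Four stronger readings are tempting and not supported.
- A reader might infer that PBO BL holds only children who never reverted. The rule is receipt of blinded placebo only. A child who reverts and leaves before switching stays in PBO BL, as does a non-seroconverter left on blinded drug.
- A reader might infer that the worst flares leave the placebo column. A child rescued directly from blinded placebo goes straight to long-term follow-up (Protocol Figure 5.3.2.1, note 5). Rescue ETV is alternative therapy (SAP 6.1) and is excluded from dose dates (SAP 8.9), so that child stays in PBO BL.
- A reader might infer that AEs leading to discontinuation migrate too. Study therapy covers blinded and open-label drug (SAP 8.9), so an AE that ends it on placebo is not followed by open-label ETV.
- A reader might infer that ETV is shown to be worse than placebo. Misplaced events would tend to act against PBO OL, but no comparison is planned and no reversion or event rate is given, so a bias of known size cannot be claimed.

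**Conclusion.** The point holds in a narrow form. In the Year 2 safety tables, AEs, SAEs and laboratory abnormalities that occur on blinded placebo between week 54 and a later switch are reported under PBO OL, and the child is missing from PBO BL because of a later event.

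About 3 to 5 of 60 placebo children could be exposed, if the planning drop-out and the 5.3% to 10% placebo seroconversion rates apply. How many revert, and when, is an assumption throughout. Over the range examined, misplaced time is 0.2% to 6% of PBO OL time, which is small. It is 4.5% to 42% of post-week-54 blinded-placebo time when 25% to 50% revert, so the damage is mainly to PBO BL. The non-seroconverter route needs a protocol deviation. Efficacy conclusions are not touched. The change is still worth making, because it is cheap and removes a misattribution that would make the Year 2 and All ETV tables disagree.

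**What to change.** For the Year 2 Safety Cohort, amend SAP 6.3 and 7.6 to split placebo children at the first dose date of open-label ETV (SAP 8.9):
- PBO OL counts time and events only from that date.
- PBO BL counts blinded-placebo time and events after the Week 48 cut up to that date, including those of children who switch later.
- The Year 2 definition of PBO BL is reworded to match. The Post-Year 1 cohorts, which use the same labels, stay as they are.
- Person-years for the exposure-adjusted rates (SAP 8.10) are split at the same date.
- A footnote identifies children who appear in both columns.

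The cost is SAP wording and one date condition, with no new data, visits or change to treatment. The downside is that a few children appear in two columns with short and unequal exposure, so the two placebo denominators overlap.

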## 7 STATISTICAL ANALYSES

### 7.1 General Methods

All analyses (efficacy, safety and PK) are presented by treatment regimen, ie, ETV vs PBO, based on the appropriate cohort and dataset defined in the earlier section. For Week 48 analysis, all the endpoints are to be cut off through Week 48, unless specified otherwise.

The PK analyses are described in [Section 7.7](#). The methods described below are used to analyze safety and efficacy data.

Categorical variables are summarized either with counts and percents or with proportions (number with event divided by number evaluable) and percents, depending on the endpoint.

Continuous variables are summarized with univariate statistics (eg, n, mean, median, standard deviation, standard error, quartiles, minimum, and maximum).

Longitudinal analyses of efficacy and safety parameters use pre-defined visit week windows (see [Section 8.4](#)). Windows around planned measurement times are constructed based on the

midpoint between planned measurement visits unless specified otherwise. Data are summarized at each scheduled visit through the analysis week.

Analyses of HBV DNA use values only from the central laboratory from the Roche COBAS® TaqMan HBV Test with limit of quantitation (LOQ) of 29 IU/mL and limit of detection (LLD) of 10 IU/mL.

Analyses of laboratory tests and serology use values from the central or local laboratory. Laboratory parameters are summarized using US standard values and units. Refer to [Section 8.11](#) for conversion of select laboratory test values from the Abbott Architect system to the Roche Diagnostics Hitachi Modular system.

Formats of tables, listings and graphs are described in the Data Presentation Plan (DPP).

